1.4 Preliminary Data

1. Smoking among adults with emotional distress is a recognized tobacco health disparity.¹⁻³

Despite reductions in the prevalence of smoking over the past fifty years (currently ~15% in US),^{4,5} smoking prevalence in individuals with emotional distress (i.e., anxiety and mood disorders) is disproportionately higher (38%-45%)^{2,6,7} and has remained relatively stable over recent years.² Smokers with emotional distress (vs. those without) are less likely to quit smoking successfully⁸⁻¹³ in large part because of the **reinforcing effects of cigarettes (i.e., smoking reinforcement).**^{14,15} Incentive sensitization theory³⁰ proposes three core processes that underlie drug reinforcement: liking, wanting, and learning. Smoking is posited to be initially motivated by the *positive* reinforcing effects of cigarettes/nicotine (i.e., “*liking*”: pleasure, satisfaction) and in turn, appetitive and urgency (“*wanting*”: craving) motivation for cigarettes develops due to the reliable, immediate rewarding effect.¹⁶ Over time, smoking is maintained by the *negative* reinforcing effects (i.e., “*learning*”: relief from aversive states and stress).^{15,17} Smokers with emotional distress are particularly vulnerable to smoking reinforcement due to various biopsychological factors that contribute to deficits in emotion regulation and heightened reward processing.¹⁸⁻²⁵ Thus, there is an ongoing need for **innovative approaches to decrease smoking reinforcement** to improve cessation success in this vulnerable group.

2. A critical aspect of smoking reinforcement is the reliability, intensity, and immediacy of its rewarding effect.²⁶

We propose that these aspects of smoking reinforcement are particularly valuable to emotionally-distressed smokers who rely on cigarettes as a go-to “quick fix” strategy during certain time-sensitive contexts (e.g. acute distress, or initial smoking abstinence). For example, modification of WHEN they smoke (e.g., when stressed) and HOW they smoke their cigarette provides smokers with the ability to easily titrate/maximize the timing and intensity of the cigarette’s rewarding effect. These aspects of smoking behavior are referred to as “**puff topography**”, which can be indexed in many ways including *puff volume* (amount of carbon monoxide [CO] inhaled, mL), *puff duration* (length of time for each inhalation, sec), and *inter-puff interval* (time between inhalations, sec). Indeed, evidence indicates that both trait and state distress are related to alterations in smoking behavior. For example, smokers with emotional distress (compared to those without) smoke in a way that maximizes intensity (e.g., larger inhalations while puffing).^{27,28}

3. Puff topography is a novel “target” of smoking reinforcement in emotionally-distressed smokers.

[figure not shown]
Although puff topography has been historically studied in the context of tobacco control (i.e., reducing CO or nicotine exposure),²⁹⁻³³ we propose **puff topography as a biobehavioral target** of smoking reinforcement. We have found that topographical components of puffing (e.g., shorter inter-puff intervals, longer puff durations) are linked to heightened smoking reinforcement (wanting, liking) in emotionally-distressed smokers but not control smokers (small-medium effects).³⁴ We have also identified several cognitive-affective aspects of emotional distress (e.g., distress intolerance, negative urgency) that are related to alterations in ad-libitum and stress-precipitated puff topography.³⁵⁻³⁸ Notably, we have moved beyond the *status quo* in our approach to this work by examining puff-to-puff changes (time-varying) during smoking rather than relying on the established (normative) methods of examining average puff parameters.^{28,39,40} This method provides precision in understanding time-sensitive aspects of puff topography. For example, we found that emotionally-distressed smokers (vs. non-distressed) take larger and more rapid initial puffs at the start of a cigarette (i.e., reward immediacy and intensity) and demonstrate more persistent, stable puffs over the course of the cigarette (i.e., reward reliability).³⁵ Together, our data indicate that puff topography is a well-specified, precise, time-sensitive mechanism of smoking reinforcement. If puff topography can be “engaged” via intervention (modifiable), it would have the strong potential to reduce the reinforcing value of cigarettes in emotionally-distressed smokers.

4. An integrated psychophysiological framework to understanding puff topography (Figure 1).

Inherent in puffing behavior are corresponding changes in cardiorespiratory parameters, such as **cardiac vagal control (CVC)**, i.e., vagus nerve mediated regulation of the heart rate. Changes in heart rate that occur during inhalation and exhalation (i.e., respiratory sinus arrhythmia [RSA]) reflect CVC. When breathing is slowed to a pace that maximizes oscillations in heart rate and blood pressure (increased CVC),⁴¹ there are numerous clinical benefits,⁴² including improved self-regulation, mediated by changes in prefrontal-subcortical inhibitory circuits.^{43,44} Indeed, improved CVC promotes more flexible and adaptive responding to the environment and less hypervigilance to threat.⁴⁵ In accord, we recently proposed an integrated psychophysiological model of emotional distress and smoking⁴⁶ wherein impaired CVC observed in smokers is not only implicated in physiological homeostasis, but also in addiction-relevant processes, including higher-order cognitive processes needed for self-regulation⁴⁶ and psychological functioning (e.g., distress).⁴³ Although slowed breathing to improve CVC is often leveraged for clinical benefit, we posit that under certain time-sensitive contexts (e.g., stress), emotionally-distressed smokers puff in a style that mimics slowed breathing – maximizing oscillations in cardiorespiratory systems and *acute* self-regulatory benefits – which in turn, paradoxically enhance smoking reinforcement. Thus, we propose that puff topography is not only a behavioral determinant of smoking reinforcement, but is also physiologically-based (CVC), and together drive the reinforcing value of each puff.

[figure not shown]
5. Puff Topography Biofeedback Training (PTBT) as a novel strategy for “target engagement”. CVC’s effect on self-regulation has been leveraged in biobehavioral interventions, like heart rate variability biofeedback, which has been used to promote reductions in emotional distress⁴³ and substance craving.⁴⁷

Figure 2. CVC synchrony (left) vs asynchrony (right)

Heart rate variability biofeedback involves instructing individuals to slow their respiration rate to around 6.0 breaths/minute,⁴¹ by following a breathing pacer and/or viewing real-time respiration and heart rate wave forms, with the goal of achieving wave form *synchrony*. See **Figure 2** for an illustration of how breathing changes can influence CVC (i.e., Min/Max) by creating synchrony vs. asynchrony between heart rate (red)

Figure 1. CVC as a Theorized Mechanism of Puff Topography in Emotional Distress-Smoking Reinforcement

and respiration (green), and in turn theoretically influence reinforcement. Aligned with our proposed framework, we developed **Puff Topography Biofeedback Training (PTBT)**, a modified application of heart rate variability biofeedback, to change puff topography. Specifically, PTBT involves teaching emotionally-distressed smokers to adjust their puffing to a pace that produces **asynchrony** between heart rate and respiration, in order to **attenuate** CVC and self-regulatory, emotional, and craving-reductions associated with smoking. Aligned with the NIH's Science of Behavior Change initiative⁴⁸ and experimental medicine approach,⁴⁹ in the **current study** we propose to test whether the **identified target (i.e., puff topography)** can be **experimentally engaged** via a well-specified intervention (PTBT).

1.5 Sample Size Justification

The effects of PTBT on the outcomes of interest are unclear given that there are no prior data. However, our studies of differences in puff topography in the context of acute stress vs. control produce medium-sized effects ($ds=0.46-0.54$).³⁶ Thus, we believe a medium size effect is clinically meaningful, and therefore, the sample size was calculated to detect a medium effect size difference across training groups. **Mean Difference.** For linear regression models, a sample size of 58 is sufficient to detect a medium effect size ($f^2=.143$ [R^2 change/1-cumulative R^2] = .143) with 80% power and alpha of 0.05 via multiple regression analyses with up to 10% variance explained by the main predictor (training group) and up to 5 other covariates (e.g., sex, number of cigarettes per day, depressive/anxiety symptom severity, corresponding baseline values, and CO boost) accounting for up to additional 20% of the anticipated variance. Without any covariates in the model, a sample size of 73 is needed to detect a medium effect size ($f^2=.11$) across training groups (explaining 10% variance). **Mediation (Aim 3).** Statistical power for a mediation analysis with a single mediator was estimated using Monte Carlo power analysis for indirect effects.⁸⁶ The inclusion of mediation analyses led us to increase our sample size to $n=80$, which is sufficient for detection of indirect effects with a proportion-mediated effect size of 50%⁸⁷ (correlations between predictor, mediators, and outcome, $r=.40-.43$) with 80% power and alpha of 0.05. which we deemed sufficient given the exploratory nature of these analyses. **Taken together**, to ensure analyses are adequately powered, we propose a sample of 88 (allowing for ~8-10% attrition) with a final intended sample of 80 completers (40 per condition).

[figure not shown]

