1.3 Research Design and Methods

This study is an experimental, between-subjects test of biofeedback puff topography training (relative to sham training) in reducing stress-induced smoking reinforcement. Specifically, combustible cigarettes smokers ($n = 80$) will be randomized to receive puff topography biofeedback ($n = 40$) or sham training ($n = 40$) prior to exposure to a laboratory stressor paradigm. Stress-precipitated smoking behavior will be assessed directly after the stressor task, wherein participants will be given the instructions to smoke utilizing their assigned puff training. Smoking reinforcement will be measured using a multi-method approach, including self-report, psychophysiology, and behavioral indices (see Measures). Outcome variables include: (1) puff topography indices (averages, trajectory) and (2) reinforcer pathology indices (delay reward discounting, cigarette demand, urges, affect, and smoking enjoyment).

A. Research Procedures

See **Figure 3** for an overview of the experimental procedures. Participants will complete a telephone interview to verify key exclusion/inclusion criteria. Participants who appear to be eligible will be scheduled for a remote assessment session. If eligible following the remote session, participants will be scheduled for two in-person visits on consecutive days. For standardization (internal validity), all in-person visits will be scheduled to occur ~4hrs following the estimated time of participants' first cigarette of the day. Participants will be informed that they will smoke their second daily cigarette during the lab visit and instructed to avoid behaviors that may confound CVC (e.g., vigorous physical activity or consumption of caffeine within 2 hr; alcohol use within 12 hr).

Baseline Assessment (Remote Visit): Staff will obtain written informed consent, after which participants will complete an eligibility assessment (see **Table 1**). They will then complete the baseline assessment battery (see **Table 1**).

[figure not shown]
Training Visit (V1): Participants will be screened for final eligibility criteria (e.g., CO level) upon arrival. Assessment of self-reported affective and smoking related variables will be conducted via self-report at various times throughout the session (see the orange stars on **Figure 3**).

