1.9 Data Collection

A. Primary Data Collection

- **Location:** This project will be conducted at the Rutgers University Affective and Biological Underpinnings of Substance Use and Anxiety (ABUSA) Laboratory located on the 2nd floor of [name]. The lab space is equipped with two rooms for psychophysiological assessment with adjacent rooms for monitoring, an in-lab smoking room that is ventilated to the outdoors with an adjacent control room for monitoring. Some eligibility and baseline assessments will be conducted remotely, using video-conferencing software (e.g., HIPAA compliant Zoom or Teams platforms) and online survey collection software (e.g., Qualtrics).
- **Process of Data Collection:** Data will be collected by IRB-approved and trained research staff from both labs of the Principal Investigators, in accordance with the procedures described in detail in section 1.3. In brief, combustible cigarettes smokers with emotional distress (N=88) will be randomized to receive puff topography biofeedback (n = 44, 50%) or sham training (n = 44, 50%) prior to exposure to a laboratory stressor paradigm. Stress-precipitated smoking behavior will be assessed directly after the stressor task, wherein participants will be given the instructions to smoke utilizing their assigned puff training. Smoking reinforcement will be measured using a multi-method approach, including self-report, psychophysiology, and behavioral indices
- **Timing and Frequency:** After the initial telephone screening, data collection will occur on one remote occasion and two in-person occasions. The remote session entails one initial assessment to confirm eligibility and collection of baseline data via interview and self-report. For the in-person visits, V1 entails data collection through self-report measures (administered at the starred time points in **Figure 3**), as well as receiving their assigned training condition. V2 will occur on the following day at the same time as V1.
- **Procedures for Audio/Visual Recording:** The diagnostic interview during the remote session will be recorded via HIPAA compliant platform (e.g., Zoom, Teams) to be used for supervision purposes as well as to ensure diagnostic fidelity.
- **Study Instruments:** **Puff topography** will be objectively measured with the *CreSS micro* (Plowshare Technologies, Borgwaldt KC, Inc), a hand-held device that has a sterilized flow meter mouthpiece that is

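### The sample size rests on a medium effect (cited ds 0.46–0.54) but is computed for 10% of variance, which is d = 0.67; 80 completers give about 53–67% unadjusted power at the cited ds, not 80%

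*Combined protocol and SAP*

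**What the plan says.** Section 1.5 first says there are no prior data on PTBT. It then turns to the group's earlier work: "differences in puff topography in the context of acute stress vs. control produce medium-sized effects ($ds=0.46-0.54". From this it concludes that a medium effect is clinically meaningful and that "the sample size was calculated to detect a medium effect size difference across training groups".

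The calculation itself is stated in variance terms, at 80% power and alpha 0.05:

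- With up to five covariates explaining up to a further 20% of variance: "a sample size of 58 is sufficient to detect a medium effect size ($f^2=.143".
- Without covariates: "a sample size of 73 is needed to detect a medium effect size ($f^2=.11$) across training groups (explaining 10% variance".

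The number was then raised to 80 completers (40 per condition) for the exploratory mediation analysis, and to 88 to allow for about 8–10% attrition. Section 6.1 plans the Aim 1 and Aim 2 regressions both with and without covariates and names neither as primary.

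The number randomized differs between sections. Section 1.3 has "smokers ($n = 80$) will be randomized to receive puff topography biofeedback ($n = 40" and 40 for sham. Section 1.9 has "will be randomized to receive puff topography biofeedback (n = 44, 50%) or sham training (n = 44, 50", and Section 1.1 also gives 88. Section 4.3 expects 90% retention across the two visits.

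**The concern.** Section 1.5 uses the word medium for two different effects. One is the standardized difference of about 0.5 from earlier studies, which is offered as the reason a medium effect matters. The other is 10% of variance explained, which is what the sample size was computed for. The section never converts one to the other. If they differ, the 80% power claim does not apply to the effect given as its basis.

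The stake is how a null result is read. Aim 1 asks whether PTBT engages its target, and Section 1.2 makes the move to efficacy testing depend on support from this study. A reader who takes the 80% at face value would treat a non-significant result as fair evidence against a difference of about half a standard deviation.

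A smaller problem is that 80 means randomized in Section 1.3 and completers in Sections 1.5 and 4.3.

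**Working it through.** **Inputs.** All come from Section 1.5: cited d = 0.46–0.54; group R² = 0.10; five covariates adding R² = 0.20; 80% power; alpha 0.05; 80 completers, 40 per arm. Sidedness is not stated. The one-degree-of-freedom F test used for a regression term is equivalent to a two-sided t test, so two-sided 0.05 is used.

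**Method.** Noncentral F test for one term in a regression with p predictors: numerator df = 1, denominator df = N − p − 1, noncentrality λ = f²·N.

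**1. Reproduce the plan's figures.**
- No covariates: f² = 0.10/0.90 = 0.111, p = 1. The smallest N with 80% power is 73 (power 0.802).
- Five covariates: f² = 0.10/(1 − 0.30) = 0.143, p = 6. The smallest N is 58 (power 0.806).
- Attrition: 80/(1 − 0.09) = 87.9, so 88.

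All three match, so the arithmetic from the stated inputs is sound.

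**2. Put both effects on one scale.** For two equal arms, R² = d²/(d² + 4) and f² = d²/4 (no covariates), so d = 2√f².

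| Effect | d | R² | f² (no covariates) |
|---|---|---|---|
| Cited, lower end | 0.46 | 5.0% | 0.053 |
| Midpoint | 0.50 | 5.9% | 0.063 |
| Cited, upper end | 0.54 | 6.8% | 0.073 |
| Used in the calculation | 2√(1/9) = 0.667 | 10.0% | 0.111 |

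The effect used exceeds the cited ones by 0.667/0.54 = 1.23 to 0.667/0.46 = 1.45, that is by 23–45%.

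**3. Power with 80 completers.** The adjusted column uses p = 6 and f² = R²/(1 − R² − 0.20).

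| d | Unadjusted | Adjusted, covariates explain 20% |
|---|---|---|
| 0.46 | 52.9% | 62.7% |
| 0.50 | 59.8% | 70.1% |
| 0.54 | 66.5% | 76.7% |
| 0.667 | 83.8% | 91.6% |

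At the cited ds the unadjusted test misses the effect in 33.5% to 47.1% of trials. If all 88 randomized participants completed, unadjusted power would still be only 56.9% (d = 0.46) to 70.7% (d = 0.54).

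**4. Detectable effect.** With 80 completers, 80% power is reached at d = 0.63 unadjusted and d = 0.56 adjusted. Both lie above 0.54.

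**5. Number randomized.** With 90% retention, 88 × 0.9 = 79.2, about the intended 80. If only 80 were randomized, as Section 1.3 reads, 80 × 0.9 = 72, one short of the no-covariate requirement of 73. Unadjusted power at the cited ds would then be 48.6% to 61.8%.

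**The case against.** **The target is printed openly and the arithmetic is right.** Section 1.5 states f² and the 10%, and at that effect 80 completers give more than 80% power. This stands, and it means the fault is a mismatch of effect-size scales rather than a slip in calculation. It does not rescue the claim, because the section derives its target from the cited ds and gives no argument for d = 0.67.

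**The ds are only an analogy.** They compare acute stress with control, not PTBT with sham, and the section does not say whether they come from between- or within-person comparisons. PTBT paces the very behaviour that Aim 1 measures, while the control arm gets no puffing instruction, so a larger Aim 1 effect is plausible. That is a fair argument for a larger target, but the plan does not make it. It also does not carry over readily to the Aim 2 outcomes, for which no prior effect is cited at all.

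**Covariates could close the gap.** They could if they explained more than assumed. At 30% of total variance, adjusted power runs from 69% (d = 0.46) to about 82% (d = 0.54); at 40%, from 76% to 88%. Those percentages are illustrative. At the 20% the section assumes, power stays below 80% throughout the cited range, and the unadjusted model is also planned.

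**The 80 in Section 1.3 is probably the completer count misplaced.** This is likely, since Sections 1.1, 1.5 and 1.9 all give 88. At 8% attrition, 80 randomized would leave 73.6, and the with-covariate requirement is only 58. The 72-completer case is therefore a side point; the text still needs correcting.

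**It is a proof-of-concept study.** A modest size is defensible on those grounds. An 80% power statement that does not hold at the effect named as its basis is not.

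**Conclusion.** The concern holds. The sample sizes in Section 1.5 deliver 80% power for d = 0.67, not for the d = 0.46–0.54 from which the section takes its medium effect. With 80 completers, power at the cited values is about 53–67% unadjusted and 63–77% adjusted. No scenario the section states reaches 80% there.

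These figures assume 1:1 allocation, a two-sided 0.05 test, the cited ds read as between-group standardized differences, and, for the adjusted figures, five covariates explaining 20% of total variance. A one-sided 0.05 test would give 66–78% unadjusted (normal approximation), also below 80%. The true PTBT effect is unknown and may be larger. The finding concerns what the plan claims, not what the trial will show.

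The conflict between 80 and 88 randomized is a separate, smaller inconsistency.

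**What to change.** In Section 1.5:

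- Show the conversion R² = d²/(d² + 4), so that 10% of variance is visibly d = 0.67.
- Replace the claim of power for a medium effect with what 80 completers provide: 80% power at d = 0.63 without covariates, or d = 0.56 if five covariates explain 20%.
- Give power at the cited ds alongside: 53–67% unadjusted and 63–77% adjusted.
- If the sponsor does regard d = 0.67 as the right target, argue for it on its own grounds instead of resting it on the cited ds.

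In Section 1.3, change the number randomized to match Sections 1.1 and 1.9 (88, 44 per arm), so that 80 means completers throughout.

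The cost is protocol wording only, with no added enrolment, visits or analyses. The stated power becomes less favourable, and a null result would have to be reported with that in view.

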1.6 Study Variables

A. Independent Variables, Interventions, or Predictor Variables

1. Training Conditions: Eligible participants will then be **randomized** to either the **Puff Topography Biofeedback (PTBT)** or **Control (Sham Training)** and informed that the training will be used in V2. Block randomization will be used with biological sex (female vs. male) as a blocking variable, as sex is a known factors that influences puff topography and reinforcement.^{36,58,59} Both trainings will be time matched.

PTBT: PTBT is designed to decrease puff topography influences on smoking reward informed by heart rate variability biofeedback paradigms. Participants will be taught how to puff in a way that may feel different from their usual puffing behavior. Participants will be hooked up to a respiratory band, electrocardiogram (ECG) electrodes, and a blood volume sensor finger cuff (pulse plethysmograph) while seated in a ventilated smoking room. Following a 5-min adaptation period, they will be introduced to a breathing pacer (EZ-Air Plus; Biofeedback Foundation of Europe), which is integrated with the *Thought Technology* biofeedback interface (**Figure 4**), and taught how to use the pacer to guide the pace of their inhalation and exhalation.

Figure 4. Example of Biofeedback Display during PTBT

Participants will be taught to breathe steadily as a white ball (pacer) proceeds up the incline, and exhale as they follow the ball on the decline. They will first practice breathing normally with the pacer to ensure they understand the procedures. Then, participants will smoke following the pacer while using the CreSS micro device for a 5-min phase. To address reinforcement immediacy and intensity, the pacer will be set to a 2 sec inhalation matched with a 2 sec exhalation, for a 4 sec cycle, such that *puffing* maps onto a respiration pace of 15 breathes/min. This pace should minimize CVC (**Figure 2, right**). To address reinforcement reliability, the inter-puff-interval will vary between 10 secs and 30 secs, as the experimenter will instruct the participant when to puff. In an adjacent room, the experimenter will be able to monitor real-time displays of physiological data and observe the session via video and intercom system and provide additional training instructions, as needed. Participants will then complete a 5-min rest period.

Control: In the control condition, i.e. sham training, participants will be hooked up to the same physiological monitoring equipment and will complete a 5-min adaptation period. They will then be instructed to smoking with the CreSS device while focusing their attention during a 5-min vanilla task.⁶⁶ The task involves attending to a computer screen and counting the number of times a designated color rectangle occupies the screen. Different colored rectangles are presented one at a time, for 500ms every 10 sec, for a total of 5-min. The full color spectrum is reflected and participants are told to make their best guess about color match. Participants are asked at the end to report the number of times the designated color was observed and are not given any feedback or incentive for correct color counts. No instructions will be provided about puffing behavior. Participants will then complete a 5-min rest period.

2. Stress-Precipitated Smoking Visit (V2). Participants will return to the laboratory on the following day, at the same time, and be provided the same pre-visit instructions. Participants will be hooked up with physiological monitoring assessment while seated in the smoking lab. Next, a new consent will be presented, introducing them to the Trier Social Stress Test (TSST), which has been used in our prior/ongoing studies (R03DA041556; F31DA043934). The TSST is a well-validated laboratory paradigm that reliably induces psychological and physiological stress,⁶⁷⁻⁶⁹ including smoking craving.^{70,71} While presenting the consent form, the experimenter will explain that they will have to prepare for and deliver a speech about why they are the best candidate for a job of their choosing. To maximize anticipatory stress, participants will be introduced to a male and female confederate who will presumably observe and evaluate the speech.⁷² After a 2-min preparation period, they will be shown a video example of a speech where a participant receives negative/neutral feedback from confederates, which serves to provide participants with additional information regarding the stressful nature of the task. In our studies, this preparation/anticipatory period produces medium-large increases in negative affect in smokers (Cohen's $d = 0.60-1.30$). After the preparation period, participants are told that the confederates need additional time to trouble-shoot the camera system, and as a result they will be able to smoke before delivering the speech. Participants will be instructed that they will practice the training they learned (PTBT or Control) while they smoke and will complete the same 5-min adaptation period pre-smoking and 5-min rest period post-smoking as in V1. The stress-precipitated smoking trial will be followed by the post-smoking assessments. Participants will then be unhooked from the physiological monitoring equipment and informed that they do not actually have to give the speech. The research staff will then proceed to notify participants that they have completed the study visit. Research staff will thank participants for all of their time and effort, provide them with their respective compensation, and encourage them to contact the study staff via email or phone (contact information listed on the participant's previously provided consent form) should they have any additional questions or concerns regarding their participation.

B. Dependent Variables or Outcome Measures

Acute Clinical Outcomes: Smoking Reinforcement.

Short Hypothetical Cigarette Purchase Task (S-CPT)

Modified Cigarette Evaluation Questionnaire (mCEQ)

Target Mechanisms: Cardiac Vagal Control.

Respiratory Sinus Arrhythmia (RSA)

Target: Puff Topography (CreSS Micro).

Puff Volume (mL)

Puff Duration (seconds)

Inter-Puff-Interval (IPI; seconds)

C. Eligibility Measures

Medical History Form (MHF)

The Mini International Neuropsychiatric Interview 7.0.0 (MINI) sections C, I, J, and K.

Expired CO Breath Sample

Smoking History Questionnaire (SHQ)

Fagerström Test for Cigarette Dependence (FTCD)

